3.7.3 Data Collection

Once informed consent has been obtained by the patient's PCP, a process to record retrospective baseline and ongoing clinical data prospectively will be implemented. Patients will be also requested to complete a patient case report form and quality of life questionnaire (either paper-based or electronic format) to gather relevant demographic and socioeconomic data.

Acknowledging the age profile of AF patients in NS, it is anticipated that a proportion of

CONFIDENTIAL

participants will chose not to complete online surveys or interact with the web-based tool. Completion of the web-based survey tools and / or interacting with the web-based tool, the AF Care Partner, is not mandatory for participation; all survey tools will be available to participants in a paper-based format.

In both study arms, baseline clinical data will be captured from the patient's chart by a data abstractor via on-site visit(s). Abstractors will utilize a laptop computer or tablet to record and transmit study data to secure and password protected servers located behind a firewall at Health Information Technology Services Nova Scotia (HITS-NS). This process will be repeated at 12 months for follow-up data collection in both study arms. Follow-up data for the intervention arm will also be captured through examination of data gathered during use of the CDSS.

The majority of patients at the start of the study are expected to have a past diagnosis of AF. As the study progresses, newly diagnosed patients are anticipated to be enrolled.

Review of PCP records will be done at 12 months to ensure completeness of outcome events. Clinical event / outcomes data will also be captured via review of hospitalization records for consented patients. Patients visiting the AF clinic in Halifax will be consented and data captured during their clinic visit. See Section 4.2 for further details.

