Information to be collected on all patients will include contact details, demographic and socioeconomic characteristics, and, clinical, process of care and health outcome variables such as: Name, year and month of birth, health card number, mobile phone number, mailing address, internet access / smart-phone and social media usage, type of residence, gender, ethnicity, date of AF diagnosis, means of documentation of AF (ECG, Holter, other), medications, risk factors for AF, bleeding and stroke (based on HASBLED, CHADS2 and / or CHA2DS2-Vasc score), prior cardiovascular or other hospitalizations and ER / AF clinic / GP office visits for AF care, laboratory investigations (e.g., thyroid studies, renal function, hemoglobin, INR), referrals, alcohol use, smoking status, cardiac risk factors, other co-morbidities / past interventions and information on the patient's pharmacies of choice. Additional information that will be sought will relate to socioeconomic, quality of life and satisfaction with care (e.g., marital / employment status, annual household income, education level, care giver support, missed work, EQ-5D-5L questionnaire). See supporting data collection materials for a complete list of variables that will be captured from the patient and or the provider via Case Report / Data Collection Forms.

Table 2. Overview of variables collected during the study

Schedule Procedure	Initial Primary Care / AF Clinic Visit	Follow-up Visits	Tertiary Care (if applicable)
Visit date	X	X	X
Demographic data	X		
Medical history	X		
Investigations / Labs / Vital signs	X	X	X
Medications / Interventions	X	X	X
Socioeconomic / HRQoL	X	X	

CONFIDENTIAL

Events (including details)	X	X	X
----------------------------	---	---	---

Costs

The relevant costs for this study may include the cost associated with the development, implementation, and maintenance of the CDSS. All the health care resource utilization associated with managing and treating participating patients with AF will also be recorded. This health care resource utilization may occur in the participating primary care providers and the tertiary AF care clinic.

HRQoL

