The analysis and reporting of the trial results will follow the CONSORT Statement for cluster-randomization trials [129]. The baseline characteristics of the practices and patients will be reported by group as mean (standard deviation) or median (first quartile, third quartile) for continuous variables, depending on the distribution, and count (percent) for categorical variables. The analysis will follow the intention-to-treat (ITT) principle. The unit of randomization will be the practice. The unit of analysis will be the patient. We will use multiple imputation to handle missing data to enable ITT analysis. Multiple imputation is a Monte Carlo technique in which the missing values are replaced by $m > 1$ simulated versions, where 'm' is typically small. Each of the simulated complete datasets will be analyzed by standard methods, and the results will be combined to produce estimates and confidence intervals that incorporate missing data uncertainty [133]. We will use generalized estimating equations (GEE) – assuming exchangeable correlation structure for patients within the same practice, and adjusting for urban and rural practice types to analyse all outcomes [130]. Unlike ordinary regression techniques, GEE allows us to model the intra-practice correlation among patients within each practice. The results will be reported as the estimate of the effect, corresponding 95% confidence interval and associated p-values. All p-values will be reported to three decimal places with those less than 0.001 reported as $p < 0.001$. The criterion for statistical significance will be set a priori at $\alpha = 0.05$, and adjusted using the Bonferroni method for multiple secondary analyses. All analyses will be performed using SAS 9.4 (Cary, NC).

Sensitivity analyses: 1) There are several methods for analyzing cluster RCTs [131]. Therefore, we will perform sensitivity analyses using some of the commonly used patient-level methods such as random-intercept model and cluster-level (i.e. random- and fixed-effects meta-analytic) methods to assess the robustness of the results. 2) Given that the unit of randomization is the practice, there is a higher chance of potential imbalance of patient-level baseline characteristics. We will perform some sensitivity analysis to adjust for any potential imbalance.

HRQoL

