This statistical analysis plan follows the JAMA Guidelines for the Content of Statistical Analysis Plans in Clinical Trials ¹³. A summary of all planned analyses is provided in **Table 1**.

Blinded Analyses

All statistical analyses will first be completed using blinded treatment groups (i.e. treatment X and Y).

Presentation of Data

The trial results will be presented according to the CONSORT guidelines for randomized controlled trials (RCTs) 14 . The baseline demographic characteristics of the patients will be summarized by group, reported as a mean (standard deviation [SD]) or median (first quartile, third quartile) for continuous variables and count (percent) for categorical variables (**Tables 2**). All statistical tests will be 2-tailed with α =0.05.

Primary Outcome Analysis

The primary efficacy analysis will be an analysis to compare rates of the composite of any AF-related emergency department visit or unplanned CV hospitalization between Intervention and Usual care over 12 months, with the outcome being treated as number of events (Tables 3). The analysis will follow the intention-to-treat (ITT) principle. While the unit of randomization is the practice/physician, the unit of analysis will be the patient. We will use Generalized Estimating Equations (GEE) —assuming exchangeable correlation structure for patients within the same practice and adjusting for urban and rural practice types to analyze all outcomes¹⁵. Unlike ordinary regression techniques, GEE allows us to estimate the intra-practice correlation among patients within each practice. For time-to-event analysis this is done using frailty-models. The results will be reported as estimate of the effect—reported as hazard ratio [HR], corresponding 95% confidence interval and associated p-values. All p-values will be reported to three decimal places with those less than 0.001 reported as p<0.001. The criterion for statistical significance will be set a priori at alpha = 0.05. The answers to the five questions in the EQ-5D-5L will be converted to health utilities using the Canadian scoring algorithm¹⁶. Cost effectiveness analysis

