BLEEDING AND STROKE RISK SCORES		'	
CHA ₂ DS ₂	NOT the value REPORTED in PCP chart.		
Score - Mean (SD) Score - n (%)	CALCULATED using documented RFs.		
0			
1			
2			
3 4			
5			
6			
7			
CHA ₂ DS ₂ -VASc	NOT the value REPORTED in PCP chart.		
Score - Mean (SD) Score - n (%)	CALCULATED using documented RFs.		
0			
1			
2			
3			
5			
6			
7			
8			
9 Bleeding risk: HAS-BLED			
Score - Mean (SD)			
Score - n (%)			
1			
2			
3 4			
5			
6			

7		
7 8		
9		
COEXISTING CONDITIONS - n		
(%)		
Previous stroke, systemic	Stroke (Yes) or SE (Yes) or TIA (Yes)	_
embolism or transient	Stroke (163) of 3E (163) of 11A (163)	
ischemic attack		
Congestive heart failure	HF/LV Dysfunction (Yes)	_
Hypertension	Hypertension (Yes) or (Yes-Treated) or (Yes-	
rrypertension	Not Treated)	
Diabetes mellitus	Diabetes (Yes-Not Documented) or (Yes-Type	
Diabetes memeas	1) or (Yes-Type 2)	
Previous myocardial	MI (MM-YYYY) or (ND)	
infarction	(
Vascular disease (any)	Vascular Disease (Yes)	
CAD	CAD (Yes)	
PAD/PVD	Aortic Plaque (Yes)	
UA	PAD/PVD (Yes)	
MI	UA (date) (MM-YYYY) or (ND)	
Aortic plaque	MI (date) (MM-YYYY) or (ND)	
Valvular Heart Disease	Replacement Type (Mechanical) or Mitral	
	Stenosis Type (Moderate) or (Severe)	
Congenial Heart Disease	Congenital Heart Disease (Yes)	
OSA	OSA Dx (Yes)	
Tobacco use		
Former	Tobacco use (Former)	
Current	Tobacco use (Current)	
Alcohol abuse	Alcohol abuse (Yes)	
Pericarditis	Pericarditis (Yes)	
Pulmonary Disease	Pulmonary Disease (Yes)	
INITEDVENITIONS (DDGGEDUDES		
INTERVENTIONS/PROCEDURES		
- n (%)	Vascular Procedure (Vas)	
Vascular procedure (any) CABG	Vascular Procedure (Yes) CABG (Yes)	
PCI	PCI (Yes)	
Ablation (for flutter or AF)	AF Ablation (Yes) or Previous Ablation for Aflu	_
Ablation from matter of All	(Yes)	
Pacemaker / ICD	Pacemaker (Yes)	
Cardioversion		
# of patients	Cardioversion (Yes)	
# of events – median (IQR)	Cardioversions no.	
Bleeding History - n (%)		

Any bleeding	Bleeding History (Yes)	
Intracranial	IC-Intracerebral (Yes) or IC-Other (Yes)	
Non-intracranial	NIC-Epistaxis (Yes) or NIC-GI (Yes) or NIC-	
Non intractation	Other (Yes)	
Major bleeding	Major bleeding (Yes)	
PAST REFERRALS - n (%)	major precumb (res)	
, ,		
AF Clinic	Referred to (AF Clinic)	
Cardiologist	Referred to (Cardiologist)	
Internist	Referred to (Internist)	
Electrophysiologist	Referred to (Electrophysiologist)	
Cath ablation	Referred to (Cath Ablation)	
ED visit for AF within the last		
12 months	ER Visits (Yes)	
# of patients - n (%)	ED Visits	

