# of events - Mean (SD)	1	
	2	
	3	
	>3	
Cardiovascular-related		
hospitalization within the last		
12 months	CV Hospitalization (Yes)	
# of patients - n (%)	CV Hospitalizations	
# of events - Mean (SD)	1	
	2	
	3	
LAB VALUES)	
eGFR – ml/min	Value when Blood Work (eGFR)	
Median		
Interquartile range		
eGFR - n (%)		
< 30 ml/min		
30-50 ml/min		
> 50 ml/min		
Hemoglobin - g/L	Value when Bloodwork (Hemoglobin)	
Median	value when bloodwork (Hemoglobin)	
Interquartile range		
Platelet - µmol/L	Value when Bloodwork (platelet count)	
Median	value when bloodwork (platelet count)	
Interquartile range		
TSH - mIU/L	Value when Bloodwork (TSH)	
Median	Talle William Diodation (1911)	
Interquartile range		
INR		
CARDIAC ASSESSMENTS		 
Prior ECHO - n (%)	ECHO (Yes)	
Ejection Fraction	The calculated EF	
Licetion Fraction	THE CARCUIATED ET	

Patients with EF - n (%)		
EF -Mean (SD)		
Normal (≥ 51%)		
Slightly Reduced (41-50%)		
Moderately Reduced (31-40%)		
Severely Reduced (≤ 30%)		
Stress Test	Stress Test (Yes)	
Holder or Loop - n (%)	Holter (Yes) or Loop (Yes)	
ECG within 12 months	ECG (Yes)	

Table 3. Primary and Secondary outcomes at 12-months

Outcome (Usual Care is reference)	Interventio (N=		Usual Gro (N:	up	Primary analysis	Sensitivity analysis	
	No. of Patients	No. of Events	No. of Patients	No. of Events	HR (95% CI); p-value	IRR (95% CI), p-value	
Primary							
AF related ED visits or CV hospitalizations							
Secondary							
AF related ED visits							
Heart Failure							
Syncope/Presyncope							
TIA/Stroke							
ACS (UA/MI)							
Rate/Rhythm							
Unplanned CV							
hospitalization							
Heart Failure							
Syncope/Presyncope							
TIA/Stroke/SE							
ACS (UA/MI)							
Rate/Rhythm							
Stroke							
Ischemic							
Other							
All-cause mortality							

Table 4a: Sensitivity analysis using commonly used patient-level methods such as random-intercept model and meta-analytic cluster-level methods.

Outcome (Usual Care is reference)	Random- intercept model HR (95% CI), p- value
Primary	
AF related ED visits or	
CV hospitalizations	
Secondary	
AF related ED visits	
Unplanned CV hospitalization	

Table 5a Subgroup analysis and subgroup sensitivity analyses of primary efficacy composite Outcome

Sub-Group	HR (95% CI), Interaction term	IRR (95% CI),
(Usual Care is reference)	p-value	Interaction term p- value
Practice Location		
Rural		
Urban		
Patient Sex		
Female		
Male		
Age (years)		
<75		
≥ 75		
CHADS2		
0		
≥1		
CHADS-VASC		
0		
≥1		

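### The primary model adjusts only for urban or rural practice and leaves out each patient's prior-year AF ED visits and CV hospitalizations, giving up some power but causing no bias

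*SAP*

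**What the plan says.** The SAP, under Primary Outcome Analysis, specifies GEE with exchangeable correlation within practice, "adjusting for urban and rural practice types to analyze all outcomes". Protocol section 3.9 has the matching phrase, "adjusting for urban and rural practice types to analyse all outcomes". Besides arm, that is the only covariate.

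The SAP describes the primary outcome "with the outcome being treated as number of events", but the effect is "reported as hazard ratio [HR], corresponding 95% confidence interval and associated p-values". Its Table 3 puts the hazard ratio under the primary analysis and the incidence rate ratio (IRR) under sensitivity analysis.

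On baseline data, protocol section 3.7.3 lists "prior cardiovascular or other hospitalizations and ER / AF clinic / GP office visits for AF care" among the information to be collected on all patients. It adds: "In both study arms, baseline clinical data will be captured from the patient's chart by a data abstractor via on-site visit(s)". SAP Table 2 has a row for "ED visit for AF within the last" 12 months and one for cardiovascular-related "hospitalization within the last" 12 months, each as number of patients and number of events. The plan uses these rows only descriptively. They are not in the primary model, the subgroup list or the SAP's sensitivity analyses. Protocol 3.9 mentions a sensitivity analysis for baseline imbalance but names no covariates, and the SAP does not carry it over.

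**The concern.** A patient's own recent events of the same kind are usually among the better predictors of such events in the next year. Here the look-back and the follow-up are both 12 months, and the baseline variables closely mirror both parts of the composite. A primary model that ignores them leaves explainable patient-to-patient variation in the comparison of arms. With the sample size fixed, that lowers the chance of detecting a real effect. The issue is efficiency: it would arise even if the arms were perfectly balanced.

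**Working it through.** **Inputs.** From protocol section 3.8: control 50%, intervention 40%, two-sided alpha 0.05, 80% power, 537 per arm, ICC 0.05, 9 patients per physician. The variance inflation factor is 1 + 8 × 0.05 = 1.4. The correlation r between baseline and follow-up events is not in the documents and is assumed.

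**1. The plan's own figure.** Total n = 2 × (1.96 + 0.84)² × (0.5 × 0.5 + 0.4 × 0.6) / 0.10² = 2 × 7.84 × 0.49 / 0.01 = 768.32. Multiplied by 1.4 this is 1075.65, the protocol's 1075. The calculation takes no credit for covariates.

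**2. Starting power.** Effective n per arm = 537 / 1.4 = 383.6. With the pooled variance under the null, power = Φ{[0.10 − 1.96 × √(2 × 0.45 × 0.55 / 383.6)] / √(0.49 / 383.6)} = Φ(0.0296 / 0.0357) = Φ(0.828) = 79.6%.

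**3. Gain on a linear (risk-difference) scale.** Adjustment multiplies the residual variance by 1 − r², so the effective n becomes 383.6 / (1 − r²). This takes the reduction to be the same within and between practices.

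| Assumed r | Interval width | Power at 1075 | Total n for the same power |
|---|---|---|---|
| 0.1 | × 0.995 | 80.0% | 1064 |
| 0.2 | × 0.98 | 81.2% | 1032 |
| 0.3 | × 0.95 | 83.2% | 978 |
| 0.4 | × 0.92 | 86.1% | 903 |
| 0.5 | × 0.87 | 89.6% | 806 |

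**4. Does this carry over to other effect measures?** Simulations of 120 practices of 9 patients compared models with and without the baseline covariate. All inputs are assumed.

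| Analysis | Strength of baseline covariate | Standard error, adjusted / unadjusted | Power |
|---|---|---|---|
| Count, IRR (GEE) | count correlation 0.28 | 0.93 | 0.91 to 0.94 |
| Count, IRR (GEE) | 0.29, lower event rate | 0.94 | 0.70 to 0.75 |
| Count, IRR (GEE) | 0.59 | 0.76 | 0.82 to 0.99 |
| Any event, odds ratio (GEE) | same three scenarios | 0.99, 1.01, 1.02 | 0.76 to 0.81; 0.65 to 0.69; 0.67 to 0.77 |
| Any event, risk difference | yes/no indicator, odds ratio 2, 3, 5 | about 0.99, 0.97, 0.95 | 82.3 to 83.5%; 83.1 to 85.2%; 83.9 to 87.0% |
| Time to event, hazard ratio (Cox) | yes/no indicator, hazard ratio 2, 3 | 1.008, 1.017 | up about 1 and 5 points |

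The GEE rows rest on 150 runs per scenario, so their power figures are approximate. The last two rows used 2000 and 1500 runs per scenario. In the count models the IRR was essentially unchanged. In the odds-ratio models the standard error hardly moved, and power rose because the adjusted estimate lies further from the null.

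**5. Timing.** Protocol section 3.7.1 gives practices their allocation when they are recruited. Patients consent later, and section 3.7.3 starts baseline abstraction after consent. A look-back that ends at consent can therefore include events that occurred after allocation.

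**The case against.** The strongest objection concerns scale. A reader might infer that adjustment would narrow the primary confidence interval. The documents do not support that, because the SAP reports a hazard ratio. Hazard and odds ratios are non-collapsible: adjusting for a prognostic covariate changes the quantity estimated and need not shrink its standard error, as the last table shows. This stands. Only the count or risk-difference form gains precision directly.

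A reader might also infer that the trial has 80% power with nothing to spare. That figure is for a two-proportion test at 9 patients per physician, not for the SAP's model. The documents also plan for 200 providers. Then 1075 / 200 = 5.4 patients each, the inflation factor is 1 + 4.375 × 0.05 = 1.22, and power is about 85% by the same formula. The figure would be lower if several providers share a practice and the practice is the cluster.

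Other points also stand:
- The baseline variables are not exact counterparts. Table 2 does not restrict hospitalizations to unplanned ones, and newly diagnosed patients may have no earlier AF visits by definition. This may weaken the association but does not disqualify a prognostic covariate.
- The present model includes the stratification factor and is valid as it is.
- The SAP is dated January 2019, after the 2014–2018 study period in protocol section 3.1, and the Table 2 shell already shows 543 usual-care patients. Changing the primary model so late needs a stated reason and must be done blind to allocation.

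**Conclusion.** The point holds as a matter of efficiency. Relevant baseline counts are collected for each patient and used only descriptively, while the primary model has a single practice-level covariate. Nothing is biased or invalid as a result.

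The size rests wholly on an assumed association: practically nil at r of about 0.1, roughly 1 to 5 power points for a modest association, and more if it is strong. The documents support no single figure. A reader might quote a power in the high eighties after adjustment, but that would need a correlation of 0.4 to 0.5, or further risk factors in the model, and neither can be shown from the documents. What form the gain takes also depends on the effect measure, which the SAP leaves unsettled by pairing an event-count outcome with a hazard ratio.

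**What to change.** Before treatment codes are broken, amend the SAP's Primary Outcome Analysis as follows:

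- Add as fixed covariates the prior-12-month number of AF-related ED visits and of CV hospitalizations (each 0, 1, 2 or more), plus age.
- End the look-back at or before the practice's randomization, or first CDSS access, so that no event after allocation is adjusted for. This needs event dates. Table 2 shows only counts, so check that dates were abstracted. If they were not and cannot be recovered, keep the covariates to a sensitivity analysis.
- Handle missing counts with the multiple imputation in protocol 3.9, and say so in the SAP, which does not repeat it.
- Name the target effect measure. If it is a hazard or odds ratio, state that the adjusted estimate is conditional.
- Report the urban/rural-only model as supportive.

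The cost is a few sentences and no new patients, plus any work needed to date the prior events. The downsides are small: the primary model is revised late, and an adjusted hazard ratio is conditional on the covariates.

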3.8 Sample Size

The primary objective of the proposed study is a composite of unplanned cardiovascular hospitalizations in AF patients and any AF-related emergency department visits. The sample size calculation is based on the test of the null hypothesis that the percentages of patients with cardiovascular hospitalizations in the two populations (CDSS and usual care) are equal. The primary measure of effect is the difference in proportions of patients with composite of any AF-related emergency department visit or unplanned CV hospitalization over 12 months. The criterion for significance (alpha) has been set at 0.05. With the proposed sample size of 1075 primary care patients (537 per intervention/control arm, assuming a 1:1 allocation ratio), the study will have power of 80% to yield a statistically significant absolute difference of 10% (or 20 [RRR] relative risk reduction) between the two percentages of patients with composite of any AF-related emergency department visit or unplanned CV hospitalization in the control and intervention groups, assuming 50% annual rate of CVD hospitalizations for the control group. This sample size was adjusted for a potential clustering of patient outcomes within a physician, by assuming an intra-physician correlation coefficient (ICC) of 0.05 with an average cluster size of 9 patients/physician. The ICC is based on studies done in the primary care sector reporting this magnitude of ICC. This extent of reduction was felt to represent a minimal clinically important achievement by a consensus of study investigators and has been an endpoint target in other studies in AF populations of similar design [127-129].

Table 3 provides a summary of the sample size calculation for different values of the baseline control rate (50%, 58%), RRR (15%, 20%, 25%, 30%), intra-class correlation coefficient [ICC] (0.05, 0.10) and average cluster size (m) (9,12,15). The primary measure of effect is the difference in the proportions or percentages of patients with cardiovascular hospitalizations and AF-related emergency room visits across study arms over an active study period of 12 months. The criterion for significance (alpha) has been set at 0.05. The test is 2-tailed, which means that an effect in either direction will be interpreted. The statistical power is set at 80%.

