The proportion of patients with reported impairment in each of the five EQ-5D-5L dimensions will be calculated for each arm. Health utilities will be calculated using the Canadian EQ-5D-5L scoring algorithm. QALYs accumulated over the study period will be calculated using the area under the curve method.

Costs

Total cost will be calculated using the sum of the product of resource utilization items (e.g. length of hospital stay, medications) and corresponding unit costs.

Cost effectiveness

The incremental cost effectiveness ratio (ICER) will be calculated by dividing the incremental difference in the mean cost between the treatment arms by the incremental difference in the mean QALYs between the arms. Sampling uncertainty is a critical issue that needs to be sufficiently and adequately dealt with in any economic evaluation alongside a clinical trial.

CONFIDENTIAL

Nonparametric bootstrap with replacement will be used to estimate the confidence intervals around the ICER. The decision uncertainty will be presented using the cost effectiveness acceptability curves in which maximum willingness to pay value from the policy maker's perspective is explicitly considered. Both base case and uncertainty analyses will be stratified by demographic and socioeconomic variables (such as age, gender and income). These stratified analyses are important for any economic evaluation to identify subpopulations that could potentially receive the most benefit from the intervention.

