will be conducted by calculating the incremental cost per QALY gained by the CDSS arm compared with the usual care arm. Due to skewness of costs and health utility distributions, the non-parametric bootstrapping method will be used to estimate the 95% confidence interval for the incremental cost per QALY gained. All analyses will be performed using SAS version 9.4 (Cary, NC).

Secondary Outcomes Analysis

We will estimate the effect of CDSS (intervention) versus usual care (control) over 12 months on the following: any AF-related emergency department visit; unplanned CV hospitalization; strokes; systemic embolism / major bleeding; mortality; anticoagulant therapy; access to specialist consultation; echo; catheter ablations; EQ5D; health care costs (Table 3). The subgroup analyses will be performed by adding an interaction term of the subgroup variable and the intervention variable in the model. The criterion for statistical significance for subgroup analyses will be set at alpha = 0.05. This will not be adjusted for multiple testing as these analyses are exploratory.

Sensitivity Analyses

There are several methods for analyzing cluster RCTs^{17, 18}. We will conduct sensitivity analyses in two ways. Firstly, we will perform sensitivity analyses using commonly used patient-level methods such as random-intercept model method (Table 4a). Secondly, we will also perform sensitivity analyses with the outcome (composite of any AF-related emergency department visit or unplanned CV hospitalization) being treated as a count assuming a Poisson distribution (Table 2). The results will be reported as incidence rate ratio [IRR], 95% CI and associated p-value. We hypothesize that our results will remain robust to the different sensitivity analyses.

Subgroup Analyses

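### The SAP's only uncertainty summary for cost-effectiveness is a bootstrap interval for the ICER, which cannot be interpreted if the QALY differences straddle zero; the protocol's acceptability curves are not carried forward

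*SAP*

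**What the plan says.** The economic plan in the SAP is a few sentences at the end of Primary Outcome Analysis. Cost-effectiveness analysis "will be conducted by calculating the incremental cost per QALY gained by the CDSS arm compared with the usual care arm". Because costs and utilities are skewed, "the non-parametric bootstrapping method will be used to estimate the 95% confidence interval for the incremental cost per QALY gained". The SAP has no acceptability curve, cost-effectiveness plane, net-benefit measure or willingness-to-pay value, and no rule for a QALY difference at or below zero. It introduces its Table 1 with the words "A summary of all planned analyses is provided in". That table has rows for EQ5D and for health care costs, but none for cost-effectiveness.

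Protocol section 3.9 (Cost effectiveness) plans the same interval: "Nonparametric bootstrap with replacement will be used to estimate the confidence intervals around the ICER". It then adds a second summary: "The decision uncertainty will be presented using the cost effectiveness acceptability curves", with the policy maker's maximum willingness to pay taken into account. The denominator of the ratio is "the incremental difference in the mean QALYs between the arms", and nothing restricts its sign.

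**The concern.** The incremental cost-effectiveness ratio (ICER) divides a cost difference by a QALY difference, so its sign alone does not say which arm is better. A negative ratio arises when CDSS is cheaper and better, and also when it is dearer and worse. A positive ratio arises when CDSS is dearer and better, and also when it is cheaper and worse. If the bootstrap QALY differences lie on both sides of zero, sorting the ratios does not rank them from favourable to unfavourable. The ratios also become very large in both directions as the denominator nears zero. Bootstrapping deals with skewness, the SAP's stated reason for it, but not with this.

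An acceptability curve avoids the problem. For each willingness-to-pay value it reports the share of replicates in which CDSS has positive net benefit, and that share is defined whatever the sign of the QALY difference. An analyst working from the SAP alone would not produce it. At stake is the uncertainty statement for a named outcome: cost-effectiveness is in the protocol's hypothesis (2.0), in its outcome list (2.2) and among the aims in the SAP's Background. The primary clinical analysis is not affected.

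**Working it through.** **Inputs from the documents.** Protocol 3.8 gives 537 patients per arm, an ICC of 0.05 and an average cluster size of 9, so VIF = 1 + (9 − 1) × 0.05 = 1.4. The shell of SAP Table 2 shows 543 in usual care, so 537 is a realistic size.

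**The plan's own figure first.** Total n = 2 × (0.5 × 0.5 + 0.4 × 0.6) × (1.96 + 0.84)² / 0.10² = 768.32, and 768.32 × 1.4 = 1075.65. This matches Table 3 and the stated 1075. The sample size is not in dispute; it only fixes the precision used below.

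**Assumptions.** Neither document gives an SD for QALYs or an expected gain. I take SDs of 0.10 to 0.25 and show several gains. The VIF comes from an ICC assumed for the primary outcome and is borrowed for QALYs.

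**Step 1: standard error of the QALY difference.** SE = SD × √(2/537 × 1.4) = SD × 0.0722.

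**Step 2: share of replicates at or below zero.** Replicates centre on the observed difference d, so by the normal approximation the share is Φ(−d/SE). It is 2.5% when d = 1.96 × SE.

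| SD | SE | d for a 2.5% share | share at d = 0.01 | share at d = 0.02 | share at d = 0.03 |
|---|---|---|---|---|---|
| 0.10 | 0.0072 | 0.014 | 8.3% | 0.3% | 0.0% |
| 0.15 | 0.0108 | 0.021 | 17.8% | 3.2% | 0.3% |
| 0.20 | 0.0144 | 0.028 | 24.4% | 8.3% | 1.9% |
| 0.25 | 0.0181 | 0.035 | 29.0% | 13.4% | 4.8% |

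At an observed difference of zero the share is 50% for every SD.

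**Sensitivity to the borrowed VIF.** With VIF 1.0 the SEs are 0.0061 to 0.0153, the observed gain needed is 0.012 to 0.030, and the share at d = 0.01 is 5% to 26%. The picture is the same.

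**Observed and true gain.** The shares above are for an observed gain. If 0.01 were the true gain, the observed value would itself vary, and the average share over repeated trials would be Φ(−0.01/(SE × √2)): 26%, 31% and 35% at SDs of 0.15, 0.20 and 0.25.

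**Step 3: what the interval would look like.** This is an illustration with assumed values: QALY difference 0.01 (SD 0.15), cost difference 300 (SD 8,000), correlation −0.2, VIF 1.4 for both, 200,000 simulated pairs.
- The 2.5th and 97.5th percentiles of the ratio are about −522,000 and +555,000 per QALY. A Fieller interval is unbounded.
- About 41% of the ratios are negative. About 65% of those have CDSS cheaper and better, and about 35% have it dearer and worse.
- At an illustrative threshold of 50,000 per QALY, the share of pairs with positive net benefit is 0.59, a well-defined point on an acceptability curve.
- With a QALY difference of 0.05 and all else equal, practically no pair has a negative QALY difference. The percentile interval is about −16,300 to +35,800 and can be read normally.

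**The case against.** The strongest reply is that the two documents should be read together. The SAP's economic text is very short. It also leaves out the protocol's area-under-the-curve QALY method, its total-cost formula and its stratified economic analyses, and it nowhere says that it replaces section 3.9. A reader might infer that the acceptability curves have been abandoned. The documents do not support that: the SAP is silent, and the protocol text still stands. What remains is that the SAP claims a complete summary of planned analyses in Table 1 and includes neither the curves nor a reference to them.

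A reader might also infer that an ICER interval never has a meaning. That is too strong. If essentially all replicates have a QALY difference of one sign, the ratios are ordered and the interval is usable, as the last illustration shows.

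It can also be said that the SAP does not commit to percentile limits or to any way of ordering replicates. That is true. But any interval for the ratio needs a rule for a denominator that crosses zero, and none is given; in the first illustration the Fieller interval fails as well.

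Finally, EQ5D and health care costs are analysed separately, which would help to show the direction of each component. They do not replace a joint statement on cost per QALY. The primary research question (2.1) does ask about costs and resource use rather than an ICER, which limits the weight of the point.

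**Conclusion.** The concern holds as a conditional defect together with an omission. As written, the SAP can produce an uninterpretable interval as its only statement of uncertainty on cost-effectiveness, and it leaves out the protocol summary that would remain valid.

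Whether the defect appears depends on the observed QALY gain relative to a threshold of about 0.014 to 0.035 over 12 months. That range rests on the assumed SDs of 0.10 to 0.25 and the borrowed VIF. It is tempting to say that an uninterpretable interval is very probable. The documents do not support that, because they give neither the expected gain nor the SD: at an observed gain of 0.03 the share of replicates at or below zero is at most about 5%, while at 0.01 it is about 8% to 29%. The reasoning about signs does not depend on these assumptions. This is a worthwhile improvement to a secondary analysis and does not threaten the trial's main conclusion.

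**What to change.** In the economic part of the SAP:
- carry forward the acceptability curve from protocol 3.9;
- add incremental net monetary benefit with a 95% confidence interval over a stated willingness-to-pay range, and a scatter of replicates on the cost-effectiveness plane;
- report a confidence interval for the ICER only if essentially all replicates have a QALY difference of one sign, with the cut-off written down (for example, no more than 2.5% of replicates on the other side of zero), and otherwise give only the ICER point estimate;
- add a cost-effectiveness row to SAP Table 1.

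Protocol 3.9 plans the ICER interval without conditions, so it should be aligned at the same time; otherwise the change creates a new difference between the documents. Everything comes from the same bootstrap replicates, with no new data and no change to the primary analysis. The cost is small but not nil: neither document gives willingness-to-pay values, and the sponsor must state them before results by arm are known.
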